4.1.2. Primary endpoint

The primary endpoint of the study is the success rate of “In-Clinic LVAT” test.

The success is defined by a LV threshold value identified automatically by “In-Clinic LVAT” feature equivalent to the manual threshold test value performed by physician on at least 90% among complete tests (performance goal).

For the primary endpoint, the evaluation is performed on 5 LV pacing vectors common to IS1 and IS4 leads: LV bipolar, LVring-RVcoil, LVtip-can, LVtip-RVcoil, and LVring-can pacing vectors. Test will be evaluated at different pacing conditions: DDD A-test and VVI. Results will be analyzed irrespective of the type of lead used (bipolar or quadripolar) and in any test configuration (DDD A-test or VVI).

An equivalent LV threshold value is defined as the same value of automatic and manual LV threshold tests, with a flexibility of ± 2 steps (meaning $\pm 0.5V$ if threshold $< 2.5V$, else $\pm 1V$ as measured in 2 consecutive cardiac cycles). A margin of ± 2 steps is accepted because of the variability of the threshold, and due to the design of the algorithm.

Among all the eligible complete LV Vector Tests collected, only those performed in DDD A-test with atrial overdrive pacing configuration (if available, otherwise in VVI) and with a manual LV threshold test performed in the same conditions and reported in the electronic Case Report Form (eCRF) will be retained. Only one LV Vector Test per LV pacing vector per subject will be analyzed.

In case several LV Vector Tests were eligible with the same LV pacing vector, for the same subject, on 2 different follow-ups, only M0 data will be considered.

The primary analysis is based on at least 231 complete LV Vector Tests provided by the algorithm and collected at M0. If data at M0 is unavailable, then corresponding data collected at M1 will be considered.

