5.4. FEATURE USE

The “In-Clinic LVAT” function is capable to measure automatically the pacing threshold values of all LV pacing vectors selected by the physician, instead of a one by one manual test (as performed in routine practice). It is composed of several consecutive individual tests called LV Vector Tests.

Before launching this function, the physician needs to program a temporary configuration comprising of a pacing configuration, starting pacing amplitude, and pacing width.

Thereafter, all LV Vectors Tests are performed sequentially. More precisely, the LV Vector Test 1 starts by launching the function and decrementing automatically the LV pacing amplitude, in order to determine the threshold value. In turn, the following LV Vector Test is automatically launched by modifying automatically the LV pacing vector programming, and so on until the last LV Vector Test. All these steps are performed automatically, and results are displayed on the programmer screen to be exploited by the physician.

Flowchart of test functioning:

“In-Clinic LVAT” tests are detailed in the Investigator Brochure (Appendix A).

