8. STATISTICAL CONSIDERATIONS

The statistical analysis will be performed as mentioned in this CIP and detailed in the Statistical Analysis Plan (SAP). Endpoints and time points are described in the other CIP sections.

Any relevant major change to the statistical analysis requested after CIP approval must be defined and approved through a CIP amendment or must be clearly mentioned in the statistical plan of the study in a section 'Changes in the conduct of analyses from CIP', including the rationale of changes.

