8.1. SAMPLE SIZE CALCULATION

The study primary objective will be met in case the null hypothesis that the success rate of the "In-Clinic LVAT" is at least than 90% is be rejected.

The statistical analysis of primary endpoint will be performed on the ITT population (see section 8.2).

A sample size of at least 231 evaluable LV pacing vectors (configuration) will provide 80% power to reject the trial null hypothesis by using a one-sided alpha 2.5% and assuming an expected success rate of 95% – configuration based. As each subject can provide data on 5 different pacing vectors, 47 (~231/5) subjects are needed for the statistical analysis. Accounting for a global attrition rate of 20%, 59 subjects shall be enrolled.

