8.5. ANALYSIS OF PRIMARY, SECONDARY AND ANCILLARY ENDPOINTS

8.5.1. Primary endpoint

The trial null hypothesis is that the success rate of the “In-Clinic LVAT” feature is lower than 90%. The alternative hypothesis is that the success rate of the “In-Clinic LVAT” feature is at greater than or equal to 90%.

The Primary endpoint is discussed in details in Section 4.1.2.

A one-sided exact binomial test for proportion at 2.5% level of significance (alpha) will be performed to test the null hypothesis for the primary endpoint. The null hypothesis will be rejected if the p-value is less than 0.025.

Handling of Missing values/censoring/Discontinuations

The primary endpoint will primarily be based on the completed LV Vector Tests provided by the algorithm and collected at M0. If data at M0 is unavailable, then corresponding data collected at M1 will be considered. If data at both M0 and M1 is missing, no imputation will be done.

Supportive Analysis of the Primary Endpoint

- i. The estimate of the success rate will be presented along with exact 95% confidence interval (CI) (Clopper & Pearson, 1934). [2]
- ii. Bayesian analysis will be performed to calculate the probability that the success rate is greater than or equal to 90%. A non-informative prior for the success rate ($\sim \text{Beta}(1, 1)$) will be assumed. Thus, if x successes out of n completed LV vector tests is observed, then success rate will have a posterior distribution $\text{Beta}(x+1, n-x+1)$. A 95% credible interval will also be calculated for the success rate.

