2.3. SAMPLE SIZE CALCULATION

The study primary objective will be met in case the null hypothesis that the success rate of the “In-Clinic LVAT” is lower than 90% is rejected.

The following assumptions were made to calculate the sample size:

- Power = 80%
- One-sided alpha = 2.5%
- Null Hypothesis proportion of success-rate (target) = 90%

LEVEA – Statistical Analysis Plan

- Expected success-rate = 95%

With these assumptions, it is required to carry out at least 231 LV vector tests. As we will have 5 different pacing vectors for each subject, we will need 47 ($\sim 231/5$) subjects.

An attrition rate of 20% is expected for this study.

Thus the number of subjects needed to be enrolled to obtain 47 evaluable subjects = $47/(1-0.2) = 59$ subjects.

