9.1.2. STATISTICAL TEST OF PRIMARY ENDPOINT

The Null hypothesis: Success rate of the “In-Clinic LVAT” feature $< 90\%$.

The alternative hypothesis: Success rate of the “In-Clinic LVAT” feature $\geq 90\%$.

Each LV vector test will be categorized as a success if the automatic and manual LV threshold test has an equivalent LV threshold value, and failure otherwise. The definition of an equivalent LV threshold value is provided above in Table 4.

The success rate of “In-Clinic LVAT” test is defined as: Number of successes/Total Number of completed LV vector tests (excluding the tests for which Manual test is missing).

A one-sided exact binomial test for proportion at 2.5% level of significance (alpha) will be performed to test the null hypothesis for the primary endpoint. The null hypothesis will be rejected if the p-value is less than 0.025.

The estimate of success rate and 95% exact CI (Clopper & Pearson, 1934) will be presented.

LEVEA – Statistical Analysis Plan

DECOMPOSITION OF PRIMARY ENDPOINT SUCCESS RATE BY LV VECTOR AND BY CONFIGURATION

Total number of completed and successful LV vector tests considered for the Primary Analysis will be presented by:

- i. LV vector tests considered with DDD A-test LV pacing configuration at M0 visit. The break up of the five LV vectors will also be presented.
- ii. LV vector tests considered with VVI test LV pacing configuration at M0 visit. The break up of the five LV vectors will also be presented.
- iii. LV vector tests considered with DDD A-test LV pacing configuration at M1 visit. The break up of the five LV vectors will also be presented.
- iv. LV vector tests considered with VVI test LV pacing configuration at M1 visit. The break up of the five LV vectors will also be presented.

Only those LV tests will be considered for which manual tests are non-missing. For number of LV vector tests “completed”, the percentage will be calculated based on ITT.

For number of LV vector tests “Successful”, the percentage calculated based on number of LV vector tests “completed”.

All LV vector test results will be listed.

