9.1.3. SUPPORTIVE AND SENSITIVITY ANALYSIS FOR PRIMARY ENDPOINT

- i. Bayesian analysis will be performed to calculate the probability that the success rate is greater than or equal to 90%. A non-informative prior for the success rate ($\sim \text{Beta}(1,1)$) will be assumed. Thus, if x successes out of n completed LV vector tests (excluding the tests for which Manual test is missing) is observed, then success rate will have a posterior distribution $\text{Beta}(x+1, n-x+1)$. A 95% credible interval will also be calculated for the success rate. The prior and the posterior density function will also be plotted.
- ii. In case the number of completed LV Vector Tests (M0 and M1 combined) is less than 231 and the primary endpoint null hypothesis is rejected, Tipping Point Analysis will be performed. Primary analysis will be repeated by shifting the status of subjects with missing primary endpoint value in order to assess the combination of results which will move the performance results from significant to non-significant. A 95% CI will be presented for each shift parameter.
- iii. The Primary analysis will be repeated excluding the subjects with major protocol deviations from the subjects considered for the primary analysis.

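### The primary test and the 231-test sample size treat up to five vector tests from one subject as independent, so correlation within subjects pushes the error rate above the stated 2.5%

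*SAP*

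**What the plan says.** SAP 9.1.1 and 9.1.2 define the primary rate as successes divided by completed LV vector tests with a manual value. It is evaluated on "5 LV pacing vectors common to IS1 and IS4 leads: LV bipolar, LVring-RVcoil, LVtip-can, LVtip-RVcoil, and LVring-can pacing vectors" (Protocol 4.1.2), with one test kept per vector per subject, so a subject contributes up to five results.

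The analysis in SAP 9.1.2 is: "A one-sided exact binomial test for proportion at 2.5% level of significance (alpha) will be performed to test the null hypothesis". Protocol 8.5.1 agrees: "A one-sided exact binomial test for proportion at 2.5% level of significance (alpha) will be performed". A Clopper-Pearson interval is computed on the same pooled count. The supportive analysis in SAP 9.1.3 also uses that count: "Bayesian analysis will be performed to calculate the probability that the success rate is greater than or equal to 90" per cent, with a Beta(x+1, n−x+1) posterior.

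For size, SAP 2.3 states: "With these assumptions, it is required to carry out at least 231 LV vector tests". Protocol 8.1 converts this to subjects: "As each subject can provide data on 5 different pacing vectors, 47 (~231/5) subjects are needed for the statistical analysis". Allowing for 20% attrition gives 59 enrolled.

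**The concern.** Every one of these calculations is a binomial calculation over vector tests. It is valid only if one vector's result says nothing about another vector's result in the same subject. The plan neither states nor defends that assumption, and the design points the other way. Three of the five vectors use the LV tip and three use the LV ring, so only two LV electrodes are involved. Protocol 5.4 describes one launch under one temporary configuration: "Thereafter, all LV Vectors Tests are performed sequentially".

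Nothing elsewhere in the plan repairs this:

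- Keeping one test per vector removes repeats of a vector but leaves five results from one heart.
- The other sensitivity analyses in SAP 9.1.3 (tipping point, exclusion of major deviations) do not cluster.
- The subject-level rate in SAP 12.2 is ancillary and counts a subject as a success on any single success.

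At stake is the study's only confirmatory claim, that the 90% goal is met at one-sided 2.5%. Under positive correlation the false-positive risk exceeds that figure and the interval is too narrow. The Bayesian analysis uses the same likelihood, so it cannot reveal the problem.

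**Working it through.** **Inputs.** Null rate 90%, expected rate 95%, one-sided alpha 2.5%, power 80%, 231 tests, five per subject, 20% attrition (SAP 2.3). The ICC is in neither document; I assume a range of 0 to 0.3.

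**Reproducing the plan.** Take the smallest r with P(X ≥ r | n, 0.90) < 0.025, then the smallest n with P(X ≥ r | n, 0.95) ≥ 0.80. This gives n = 231 and r = 217, with exact alpha 2.39% and power 81.6%. Then 231/5 = 46.2, rounded up to 47, and 47/0.8 = 58.75, rounded up to 59. The plan's figures reproduce exactly under independence, so no allowance for clustering is hidden in them.

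**Adding correlation.** Let subject i have m_i tests, with successes beta-binomial: mean p and parameters a = p(1−ICC)/ICC and b = (1−p)(1−ICC)/ICC. Convolving over subjects gives the exact distribution of the total. The plan's own rejection rule is then applied.

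One-sided type I error at a true 90%:

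| Tests (subjects) | Reject at | ICC 0 | 0.05 | 0.1 | 0.2 | 0.3 | ICC at which 2.5% is passed |
|---|---|---|---|---|---|---|---|
| 231 (47) | 217 | 2.4% | 3.5% | 4.7% | 7.1% | 9.4% | 0.005 |
| 235 (47) | 221 | 2.0% | 3.0% | 4.0% | 6.3% | 8.5% | 0.028 |
| 295 (59) | 276 | 2.1% | 3.2% | 4.3% | 6.6% | 8.8% | 0.018 |
| 231 (59) | 217 | 2.4% | 3.2% | 4.1% | 5.8% | 7.6% | 0.007 |

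The result does not hang on the beta-binomial form. A logit-normal subject effect at ICC 0.05, 0.1, 0.2 and 0.3 gives 3.5%, 4.5%, 7.0% and 9.2% (231 tests) and 3.1%, 4.2%, 6.7% and 8.9% (295 tests).

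**Coverage** of the nominal 95% Clopper-Pearson interval at a true 95%, same ICCs: 93%, 91%, 86%, 82% (231 tests) and 94%, 92%, 88%, 84% (235 tests).

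**Power at a true 95%**, same ICCs:

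- Planned rule: 80%, 78%, 76%, 74% (231 tests) and 87%, 86%, 83%, 81% (295 tests). The fall is modest, but this rule no longer holds 2.5%.
- Critical count raised until 2.5% holds: 72%, 62%, 53%, 45% (231 tests, 47 subjects) and 82%, 74%, 66%, 58% (295 tests, 59 subjects).

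**Required size by simple design effect**, 1 + (5−1) × ICC:

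- ICC 0.05: 231 × 1.2 = 277.2, so 278 tests or 56 subjects.
- ICC 0.1: 231 × 1.4 = 323.4, so 324 tests or 65 subjects.
- ICC 0.2: 231 × 1.8 = 415.8, so 416 tests or 84 subjects.
- ICC 0.3: 231 × 2.2 = 508.2, so 509 tests or 102 subjects.

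**The case against.** The strongest reply is that the size of the error rests on an ICC that nobody has supplied. At ICC 0.05 the excess is only 0.5 to 1.0 percentage point; errors of 6 to 9% need an ICC of 0.2 to 0.3, and nothing in the documents points to values that large. Some features may also lower the ICC. The one subject-level cause the documents name, a long inter-ventricular conduction delay, is given as a reason for the algorithm not being applicable; such tests would tend not to complete and so leave the denominator. The ±2-step margin is justified partly by threshold variability, which could be noise at vector level.

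The crossing point also moves with the number of tests obtained. With five tests per subject and ICC 0.05, the error stays below 2.5% at 15 of the 65 counts from 231 to 295 (for example 2.39% at 240). Finally, SAP 9.1.2 breaks results down by vector and lists them all, so a reader could look for clustering.

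These points stand as limits on how precisely the excess can be stated. They do not restore the test. At the sizes that follow from the plan (231, 235 and 295) the error exceeds 2.5% at ICC 0.05, and at 231 tests the margin is used up at about 0.005. A descriptive breakdown leaves the decision rule unchanged. It is also fair that the remedy should be a single named method, and that its power cost under independence should be disclosed.

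**Conclusion.** The concern holds. The primary test, its interval, the Bayesian posterior and the sample size all assume independence within subjects, and the plan neither states nor protects that assumption. With an ICC of 0.1 to 0.2 the true one-sided error is about 4 to 7%, roughly 1.6 to 2.8 times the stated level, and interval coverage is about 86 to 92%. The stated 80% power belongs to a test that does not hold its level.

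That the plan assumes independence is a fact of the text. That correlation is positive is an inference from the design. Its size is an assumption, shown as a range. Because this is the sole confirmatory test against a fixed goal, it must be fixed.

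**What to change.** **SAP 9.1.2 and Protocol 8.5.1.** Declare success if a one-sided 97.5% lower limit, with the subject as cluster, exceeds 90%. I suggest naming one method: Clopper-Pearson with the Korn-Graubard effective sample size. With K subjects, n tests and y_i successes in m_i tests:

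- p̂ = Σy_i/n and v = [K/(K−1)] Σ(y_i − m_i p̂)²/n².
- n* = [p̂(1−p̂)/v] × (t_{n−1}/t_{K−1})², using 97.5% t quantiles and capped at n.
- Apply Clopper-Pearson to n* and n*p̂.

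State in advance what happens if v is zero. In simulation the type I error is 1.4 to 3.1% over ICC 0 to 0.3 (up to 3.3% under a logit-normal model); this residual excess should be stated. If stricter control is wanted, a 98.25% limit gives 0.9 to 2.3% (up to 2.7% logit-normal) and costs about 4 to 8 points of power. Report the pooled exact test and pooled posterior as descriptive.

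**Protocol 8.1 and SAP 2.3.** Say that 231 tests from 47 subjects give 80% power only for the pooled test under independence, and give the power of the clustered test:

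| Evaluable subjects | ICC 0 | 0.05 | 0.1 | 0.2 | 0.3 |
|---|---|---|---|---|---|
| 47 | about 75% | 66% | 59% | 49% | 41% |
| 59 | about 86% | 78% | 71% | 59% | 50% |

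For 80% power with this method, about 62, 74, 94 and 114 evaluable subjects are needed at ICC 0.05, 0.1, 0.2 and 0.3. These exceed the simple design-effect figures.

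**Documentation.** Protocol 8 says: "Any relevant major change to the statistical analysis requested after CIP approval must be defined and approved through a CIP amendment", or else set out with its rationale in the SAP's section on changes. SAP 3.1 currently records none. SAP 17.8 names an extract whose file name carries 20180112, before SAP 1.0 of 19 February 2018. The reason for the change should therefore be recorded and the pooled result still shown.

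**Lower priority.** Use subject-clustered intervals for the pooled descriptive rates in SAP 10.1 to 10.3, 11.1B and 12.1.

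**Cost.** A documented change to the primary test, with text and code. No new data or subjects are needed to run the analysis, but the interval will usually be wider and the stated power lower.

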9.1.3. SUPPORTIVE AND SENSITIVITY ANALYSIS FOR PRIMARY ENDPOINT

- i. Bayesian analysis will be performed to calculate the probability that the success rate is greater than or equal to 90%. A non-informative prior for the success rate ($\sim \text{Beta}(1,1)$) will be assumed. Thus, if x successes out of n completed LV vector tests (excluding the tests for which Manual test is missing) is observed, then success rate will have a posterior distribution $\text{Beta}(x+1, n-x+1)$. A 95% credible interval will also be calculated for the success rate. The prior and the posterior density function will also be plotted.
- ii. In case the number of completed LV Vector Tests (M0 and M1 combined) is less than 231 and the primary endpoint null hypothesis is rejected, Tipping Point Analysis will be performed. Primary analysis will be repeated by shifting the status of subjects with missing primary endpoint value in order to assess the combination of results which will move the performance results from significant to non-significant. A 95% CI will be presented for each shift parameter.
- iii. The Primary analysis will be repeated excluding the subjects with major protocol deviations from the subjects considered for the primary analysis.

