3.2. SAP AMENDMENT/ADDENDUM RATIONALE AND CHANGE HISTORY

Version	Date	Section(s)	Description of modifications
1.0	19Feb2018		
Initial Release.
 
Updated Sections: 5.7, 9.1.1, 9.1.2, 9.1.3, 10.2, 10.4, 11.1, 12.2, 13.5

1.1	13 Mar		
It was clarified that for end-points requiring comparison of the algorithm threshold value with the manual threshold value, only those LV tests will be considered for which a non-missing manual threshold value is available.
 
In Section 9.1.1 it is mentioned that only Complete LV tests will be considered to be included in the Analyses, thus number of Attempted will be same as number of completed.
 
Hence, for Decomposition of the success rate of the Primary Endpoint, the number of attempted is redundant and will not be presented. The percentage for Completed LV tests will be calculated based on ITT.

			
Some editorial changes (eg. changing “patient” to “Subject”) and additional clarifications (eg. The six and eight LV tests considered for IS1 And IS4 and only IS4 leads respectively) have also been provided.

1.2	10 Apr		
Updated Sections: 11.1 B, 11.1 C
 
The reasons for “LV pacing threshold underestimation” and “LV unexpected assessment” will be provided as additional information to understand the underlying causes of under-estimated and

LEVEA – Statistical Analysis Plan

unexpected assessments.

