9. PRIMARY EFFICACY ANALYSES

9.1. PRIMARY ENDPOINT ANALYSIS

9.1.1. PRIMARY ENDPOINT

The primary endpoint of the study is the success rate of “In-Clinic LVAT” test, that is the (Number of successes/Total Number of completed LV vector tests excluding the tests for which Manual tests are missing) of the “In-Clinic LVAT” feature.

For the primary endpoint, the evaluation is performed on 5 LV pacing vectors common to IS1 and IS4 leads:

Table 7: LV tests for Primary Endpoint

#	IS1 lead	IS4 lead
1	LVtip-LVring	LVtip1-LV2
2	LVtip-RVcoil	LVtip1-RVcoil
3	LVtip-CAN	LVtip1-CAN
4	LVring-RVcoil	LV2-RVcoil
5	LVring-CAN	LV2-CAN

Test will be evaluated at different LV pacing conditions: DDD A-test and VVI test. Among all the eligible complete LV Vector Tests collected, only those performed in DDD A-test with atrial overdrive pacing configuration (if available, otherwise in VVI) and with a manual LV threshold test performed in the same conditions (same pacing pulse width) and reported in the electronic Case Report Form (eCRF) will be retained. In case several LV Vector Tests were eligible with the same LV pacing vector, for the same subject, on 2 different visits, only M0 data will be considered.

The primary analysis is based on manual tests which are non-missing and for which complete LV Vector Tests are provided by the algorithm and collected at M0. If data at M0 is unavailable, then corresponding data collected at M1 will be considered.

To summarise, the following table mentions the adequate LV pacing configuration to be considered for the LV Vector test for the Primary Analysis:

Table 8: LV tests for Primary Analysis

Cases	Visit	LV pacing Configuration		Which one to use?
		DDDA-test	VVI test	

LEVEA – Statistical Analysis Plan

Cases	Visit	LV pacing Configuration		Which one to use?
		DDD-test	VVI test	
Case 1	M0	Available	Available	Use DDD A-test
Case 2	M0	Available	Unavailable	Use DDD A-test
Case 3	M0	Unavailable	Available	Use VVI test
Case 4	M0	Unavailable	Unavailable	Go to M1
	M1	Will be considered only for Case 4		
Case 5	M1	Available	Available	Use DDD A-test
Case 6	M1	Available	Unavailable	Use DDD A-test
Case 7	M1	Unavailable	Available	Use VVI test
Case 8	M1	Unavailable	Unavailable	Unavailable

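### The only tipping-point analysis of the primary endpoint is gated on a count of 231 tests, which does not measure how many outcomes are missing

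*SAP*

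**What the plan says.** SAP 9.1.3 item ii sets two conditions that must both hold. The first is the count: "In case the number of completed LV Vector Tests (M0 and M1 combined) is less than 231". The second is a positive result: "the primary endpoint null hypothesis is rejected, Tipping Point Analysis will be performed". The method follows: "Primary analysis will be repeated by shifting the status of subjects with missing primary endpoint value".

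The figure 231 comes from the power calculation. SAP 2.3 states: "With these assumptions, it is required to carry out at least 231 LV vector tests". Protocol 4.1.2 and the synopsis use it as a data requirement: "The primary analysis is based on at least 231 complete LV Vector Tests provided by the algorithm and collected at M0", with M1 data as the fallback.

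The endpoint is scored per test, not per subject: "Each LV vector test will be categorized as a success if the automatic and manual LV threshold test has an equivalent LV threshold value" (SAP 9.1.2). Its denominator is "completed LV vector tests excluding the tests for which Manual tests are missing" (SAP 9.1.1). That exclusion is repeated in 9.1.2 and in item i of 9.1.3, but not in item ii.

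Protocol 8.5.1 plans no imputation when both visits are missing. The other items of 9.1.3 are a Bayesian analysis on the same observed counts and a repeat without subjects who have major deviations. Neither varies a missing outcome.

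**The concern.** A tipping-point analysis asks how badly the missing outcomes would have to turn out before the conclusion changes. Whether it is needed depends on how many outcomes are missing and how close the result is to the boundary. The 231 condition reflects neither. It shows whether the planned amount of data was reached, and that is a question of power.

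Two consequences follow.

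- With 231 or more completed tests and a rejected null, no missing-data check is planned, however many outcomes are missing.
- The SAP's definition of a complete test (5.7) does not require a manual value. Taken literally, a completed test with no manual value is dropped from the primary denominator but still counts towards 231. A missing outcome then helps to switch the check off.

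At stake is the supporting evidence for a positive result. The primary test itself is unaffected.

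**Working it through.** **Inputs.** Null rate 90%, expected rate 95%, one-sided alpha 2.5%, power 80%, five vectors per subject, 20% attrition (SAP 2.3). One-sided exact binomial test (SAP 9.1.2). Tests are treated as independent, as in the SAP.

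**Reproducing 231.** The p-value is P(X ≥ x) for X ~ Binomial(n, 0.90). The critical value c(n) is the smallest x with p < 0.025. At n = 230, c = 217 and power at 95% is 0.737. At n = 231, c = 217, exact alpha is 0.0239 and power is 0.816. So 231 is the first n that reaches 80% power. Then 231/5 = 46.2, rounded up to 47, and 47/0.8 = 58.75, rounded up to 59. The plan's figures are confirmed, and 231 is purely a power figure.

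**What the gate responds to.**
- 46 subjects with all five vectors complete and a manual value for each give 46 × 5 = 230 tests. Nothing is missing among them, yet the count condition is met.
- 231 completed tests of which 10 lack a manual value leave 231 − 10 = 221 in the primary denominator. On a literal reading the condition is not met.

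**Reversal.** With x successes in n evaluable tests and m missing, let f of the missing fail and the rest succeed. Significance is lost at the smallest f with x + m − f < c(n + m). The last column of the table is P(F ≥ f) for F ~ Binomial(m, q), where q is the observed failure rate: 11/231 = 4.8% for 220/231 and 14/231 = 6.1% for 217/231. The observed p-values are 0.0029 for 220/231 and 0.0239 for 217/231.

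Main scenario: the missing outcomes are completed tests without a manual value. The documents give no expected number, so m = 10 and m = 20 are assumptions.

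| Observed | m | c(n+m) | f needed | Result at f | p | P(F ≥ f) |
|---|---|---|---|---|---|---|
| 220/231 | 10 | 227 | 4 (40%) | 226/241 | 0.027 | 0.1% |
| 220/231 | 20 | 236 | 5 (25%) | 235/251 | 0.030 | 0.2% |
| 217/231 | 10 | 227 | 1 (10%) | 226/241 | 0.027 | 46% |
| 217/231 | 20 | 236 | 2 (10%) | 235/251 | 0.030 | 34% |

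Wider scenario: every unfilled slot of the five primary vectors counts as missing. If all 59 subjects are in ITT there are 59 × 5 = 295 slots, so 295 − 231 = 64 (21.7%) are unfilled. With 47 subjects there are 47 × 5 = 235 slots and 4 are unfilled. These counts include incomplete and never-launched tests, which the declared endpoint leaves out.

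| Observed | Slots | m | c(n+m) | f needed | Result at f | p | P(F ≥ f) |
|---|---|---|---|---|---|---|---|
| 220/231 | 295 | 64 | 276 | 9 (14%) | 275/295 | 0.035 | 0.3% |
| 217/231 | 295 | 64 | 276 | 6 (9.4%) | 275/295 | 0.035 | 19% |
| 220/231 | 235 | 4 | 221 | 4 (100%) | 220/235 | 0.035 | below 0.1% |

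In none of these rows would the planned check run.

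**The case against.** **The gate has a purpose.** The protocol bases the primary analysis on at least 231 complete tests, and the SAP adds a check for the case where that minimum is missed. This is coherent, and no document requires a check in other circumstances. It stands as an explanation of the rule. It does not make 231 a measure of missingness.

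**A reader might infer that a passing result could rest on more than a fifth of the data being missing.** The documents do not support that. The endpoint is defined among completed tests with a manual value. Tests that were launched without yielding a value, or never launched, lie outside it, and completeness is assessed separately under applicability (Protocol 4.1.3 d, SAP 10.4). The 64 unfilled slots also need all 59 subjects in ITT, whereas the plan expects about 47 evaluable. This objection stands, so the slot figures are only a secondary scenario.

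**A reader might also infer that results near the expected 95% are fragile.** They are not. At the observed failure rate, each 220/231 case shown has a reversal probability below 0.5%. The missing tests would have to fail about three or more times as often as the observed ones. Fragility is real near the boundary, where p = 0.024 and the exact confidence interval would already signal a marginal result.

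**Much of the loss is reported elsewhere.** SAP 9.1.2 shows no attempted tests for the primary endpoint: "Hence, for Decomposition of the success rate of the Primary Endpoint, the number of attempted is redundant and will not be presented" (SAP 3.2). But SAP 10.1 and 10.2 give attempted and completed counts by vector and configuration at M0, and 11.1 C gives them by visit. Comparing the completed counts of 10.1 with those of 10.2 approximates the number without a manual value at M0. All test results are also listed. This largely stands. However, those tables do not apply the rule of one test per vector per subject, and they do not show how many failures would change the conclusion.

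**Conclusion.** The point holds in a limited form. The sole planned analysis of missing primary outcomes depends on an absolute count taken from the power calculation, so it is not run at 231 or more tests whatever the amount of missing data. On a literal reading, completed tests without a manual value help to switch it off. The wording that shifts subjects does not match an endpoint scored per test. This and the omitted manual-value exclusion are best read as drafting slips, since 9.1.1 and 9.1.2 make the intention clear.

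The size depends on the result. With 10 or 20 missing manual values (assumed), 220/231 would be very hard to overturn, while 217/231 would be overturned by a single failure in 10. The figures treat tests as independent and count the remaining missing tests as successes. The documents do not support a claim that the primary conclusion is unsound or that the rule conceals a fragile result. This is a minor, worthwhile improvement to a supportive analysis.

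**What to change.** Amend SAP 9.1.3 item ii as follows.

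- Delete the 231 condition. Run the tipping point whenever the null hypothesis is rejected and any primary outcome is missing.
- Shift the status of individual LV vector tests, not subjects, over the five primary vectors of the ITT subjects. Use the 9.1.2 denominator rule and the same one-sided exact binomial test.
- Make completed tests without a manual value the main scenario.
- Show launched-but-incomplete and never-launched tests separately, labelled as answering a different question from the declared endpoint.
- Report the number and share of missing tests that must fail for significance to be lost, next to the observed failure rate.
- Add the manual-value exclusion to item ii so that it matches 9.1.1, 9.1.2 and item i.

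The cost is a short wording change and a little programming on data already in the device files and the eCRF. The downside is one more supportive result that may look less favourable. The primary endpoint, its test and the decision rule do not change.
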